8.3.2 Direct access to source data and documents

The investigator /institution will allow site trial-related monitoring, audits, IRB/IEC review and regulatory inspections. Direct access must be provided to the CRF and all source documents/data, including progress notes, copies of laboratory and medical test results, which must be available at all times for review by the CRA, auditor and regulatory inspector (e.g. Food and Drug Administration (FDA)). They may review all CRFs and informed consents. The accuracy of the data will be verified by direct comparison with the source documents described in [Section 8.3.1](#). The sponsor will also monitor compliance with the protocol and GCP.

8.3.3 Storage period of records

Trial site(s):

The trial site(s) must retain the source and essential documents (including ISF) according to contract or the local requirements valid at the time of the end of the trial (whatever is longer).

Sponsor:

The sponsor must retain the essential documents according to the sponsor's SOPs.

8.4 EXPEDITED REPORTING OF ADVERSE EVENTS

BI is responsible to fulfil their legal and regulatory reporting obligation in accordance with regulatory requirements.

Exemptions from expedited reporting are described in [Section 5.2.6.2](#), if applicable.

8.5 STATEMENT OF CONFIDENTIALITY AND PATIENT PRIVACY

Individual patient data obtained as a result of this trial is considered confidential and disclosure to third Parties is prohibited with the exceptions noted in [Section 8.7](#). Patient privacy will be ensured by using patient identification code numbers.

Data protection and data security measures are implemented for the collection, storage and processing of patient data in accordance with the principles 6 and 12 of the World Health Organization (WHO) GCP handbook.

Personalized treatment data may be given to the patient's personal physician or to other appropriate medical personnel responsible for the patient's welfare. Data generated as a result of the trial need to be available for inspection on request by the Participating physicians, the sponsor's representatives, by the IRB/IEC and the regulatory authorities.

8.5.1 Collection, storage and future use of biological samples and corresponding data

Measures are in place to comply with the applicable rules for the collection, storage and future use of biological samples and clinical data, in Particular

- Sample and data usage has to be in accordance with the separate biobanking informed consent
- The BI-internal facilities storing biological samples from clinical trial Participants as well as the external banking facility are qualified for the storage of biological samples collected in clinical trials.
- An appropriate sample and data management system, incl. audit trail for clinical data and samples to identify and destroy such samples according to ICF is in place
- A fit for the purpose documentation (biomarker proposal, analysis plan and report) ensures compliant usage
- A fit for purpose approach will be used for assay/equipment validation depending on the intended use of the biomarker data
- Samples and/or data may be transferred to third Parties and other countries as specified in the biobanking ICF

8.6 TRIAL MILESTONES

The **start of the trial** is defined as the date when the first patient in the whole trial signs informed consent.

The **end of the trial** is defined as the date of the last visit of the last patient in the whole trial (“Last Patient Completed”).

The “**Last Patient Drug Discontinuation**” (LPDD) date is defined as the date on which the last patient at the trial site ends trial medication (as scheduled per protocol or prematurely). Individual investigators will be notified of suspected unexpected serious adverse reactions (SUSARs) occurring with the trial medication until 30 days after LPDD. **Early termination of the trial** is defined as the premature termination of the trial due to any reason before the end of the trial as specified in this protocol.

Temporary halt of the trial is defined as any unplanned interruption of the trial by the sponsor with the intention to resume it.

Suspension of the trial is defined as an interruption of the trial based on a Health Authority request.

The IEC/CA in the member state will be notified about the trial milestones according to the local laws.

A final report of the clinical trial data will be written only after all patients have completed the trial to incorporate and consider all data in the report.

The sponsor will submit to the EU database a summary of the final trial results within one year from the end of a clinical trial.

8.7 ADMINISTRATIVE STRUCTURE OF THE TRIAL

The trial is sponsored by Boehringer Ingelheim (BI).

The trial is conducted at a site specialized in conducting PET studies for biodistribution and tumor uptake of radiolabeled drugs.

A Coordinating Investigator is responsible to coordinate investigators at the Participating site. Tasks and responsibilities are defined in a contract.

A SMC composed of members of the trial site and members of the BI trial team will be established to review individual and aggregated data at regular intervals to assess the feasibility/specificity of the process, to evaluate the appropriacy of further enrolment in a cohort or the move to the next cohort and to support the identification of the best dose based on PET results and possible associated biomarkers. The SMC will also review safety and efficacy data to support the overall determination of the safety profile and risk/benefit ratio of the treatment.

Details of the SMC responsibilities and procedures are described in the SMC plan.

Relevant documentation on the Participating (Principal) Investigators (e.g. their curricula vitae) will be filed in the ISF. The investigators will have access to the BI clinical trial portal (Clinergize) to facilitate document exchange and maintain electronic ISF.

BI has appointed a Trial Clinical Monitor (TCM), responsible for coordinating all required activities, in order to

- manage the trial in accordance with applicable regulations and internal SOPs,

Proprietary confidential information © 2020 Boehringer Ingelheim International GmbH or one or more of its affiliated companies

- direct the clinical trial team in the preparation, conduct, and reporting of the trial,
- ensure appropriate training and information of Local Clinical Monitor (CML), Clinical Research Associates (CRAs), and investigators of Participating country.

The organisation of the trial in the Participating country will be performed by the respective local or regional BI-organisation (Operating Unit (OPU)) in accordance with applicable regulations and BI SOPs.

Data Management and Statistical Evaluation will be done by BI according to BI SOPs.

Tasks and functions assigned in order to organise, manage, and evaluate the trial are defined according to BI SOPs. A list of responsible persons and relevant local information can be found in the ISF.

External laboratory services will be used in this trial. Details will be provided in the Laboratory Manuals, available in the ISF.

10. APPENDICES

10.1 IMMUNE-RELATED ADVERSE EVENTS OF SPECIAL INTEREST

Table 10.1: 1 Immune-related adverse events of special interest

This table defines immune-related AEs that must be reported as AESIs.

Immune-related adverse events of special interest
Pneumonitis (report as AESI if an irAE is \geq Grade 2) 
• Acute interstitial pneumonitis• Interstitial lung disease• Pneumonitis
Colitis (report as AESI if an irAE is \geq Grade 2 or any grade resulting in dose modification or use of systemic steroids to treat the AE) 
• Intestinal obstruction• Colitis• Colitis microscopic• Enterocolitis• Enterocolitis haemorrhagic• Gastrointestinal perforation• Necrotizing colitis• Diarrhea
Endocrine (report as AESI if an irAE is \geq Grade 3 or \geq Grade 2 and resulting in dose modification or use of systemic steroids to treat the AE) 
• Adrenal insufficiency• Hyperthyroidism• Hypophysitis• Hypopituitarism• Hypothyroidism• Thyroid disorder• Thyroiditis• Hyperglycaemia, if \geq Grade 3 and associated with ketosis or metabolic acidosis
Endocrine (report as AESI for any grade) 
• Type 1 diabetes mellitus (if new onset)

Table 10.1: 1 (con't) Immune-related adverse events of special interest

Hematologic (report as AESI if an irAE is \geq Grade 3 or any grade resulting in dose modification or use of systemic steroids to treat the AE)

• Autoimmune haemolytic anaemia• Aplastic anaemia• Thrombotic thrombocytopenic purpura• Idiopathic (or immune) thrombocytopenia purpura• Disseminated intravascular coagulation• Haemolytic-uraemic syndrome• Any Grade 4 anaemia regardless of underlying mechanism
Hepatic (report as AESI if an irAE is \geq Grade 2, or any grade resulting in dose modification or use of systemic steroids to treat the AE)

• Hepatitis• Autoimmune hepatitis• Transaminase elevations (ALT and/or AST)
Infusion Reactions (report as AESI for any grade)

• Allergic reaction• Anaphylaxis• Cytokine release syndrome• Serum sickness• Infusion reactions• Infusion-like reactions
Neurologic (report as AESI for any grade)

• Autoimmune neuropathy• Guillain-Barre syndrome• Demyelinating polyneuropathy• Myasthenic syndrome
Ocular (report as AESI if an irAE is \geq Grade 2 or any grade resulting in dose modification or use of systemic steroids to treat the AE)

• Uveitis• Iritis
Renal (report as AESI if an irAE is \geq Grade 2)

• Nephritis• Nephritis autoimmune• Renal failure• Renal failure acute• Creatinine elevations (report as an irAE if \geq Grade 3 or any grade resulting in dose modification or use of systemic steroids to treat the AE)

Proprietary confidential information © 2020 Boehringer Ingelheim International GmbH or one or more of its affiliated companies

Table 10.1: 1 (con't) Immune-related adverse events of special interest

Skin (report as AESI for any grade)

• Dermatitis exfoliative• Erythema multiforme• Stevens-Johnson syndrome• Toxic epidermal necrolysis
Skin (report as AESI if an irAE is \geq Grade 3)

• Pruritus• Rash• Rash generalized• Rash maculopapular• Any rash considered clinically significant in the physician's judgment
Other (report as AESI for any grade)

• Myocarditis• Pancreatitis• Pericarditis• Any other Grade 3 event that is considered immune-related by the physician

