As of 30 November 2018, the combination treatment has been well tolerated with no DLTs occurring during the MTD evaluation period of the dose escalation part of the trial and no treatment related deaths have been reported. The most frequently reported AEs in patients treated with combination BI 754091 and BI 754111 were nausea (23.3%), fatigue (22.2%), diarrhoea (15.1%) and vomiting (15.1%). The majority of AEs were CTCAE Grades 1 and 2. Grade 3 and 4 AEs occurred at a frequency of 24.4% and 1.2 %, respectively. Of the grade 3 AEs, colitis, diarrhea (2 cases), infusion related reaction (2 cases), aseptic meningitis and maculopapular rash were reported as possibly related to study drugs. The only Grade 5 event was respiratory failure, occurring in the context of AEs pneumonia, sepsis and progressive disease. These events (including the fatal event) were unrelated to trial drugs.

Infusion related reactions have been reported in approximately 7% of patients treated with the combination of BI 754091 and BI 754111, none reported with BI 754091 monotherapy. The majority of the events were reported in patients receiving 240 mg of BI 754091 in combination with 600 mg of BI 754111, with 2 events reported in patients receiving 240 mg of BI 754091 in combination with 20 mg of BI 754111. The majority were of CTCAE Grade 2. Two events were Grade 3 events and led to treatment discontinuation. The reported infusion related reactions occurred during the infusion mostly at cycle 2 or cycle 3.

Preliminary efficacy data show 25 patients have achieved best response of stable disease (SD) to date and 3 patients have achieved best response of partial response (PR). PR was reported for 1 patient with anal cancer treated with 240 mg BI 754091 in combination with 200 mg BI 754111, 1 patient with microsatellite stable rectal cancer treated with 240 mg BI 754091 in combination with 600 mg BI 754111 and 1 patient with Triple Negative Breast Cancer (TNBC) treated with 240 mg BI 754091 in combination with 600 mg BI 754111.

Based on these pre-clinical and clinical data treatment with BI 754111 and BI 754091 is expected to provide patients with clinical benefit at an acceptable risk.

Risk linked to radiation burden: A single injection of 37 MBq 89Zr-mAb is expected to result in a radiation burden of ~ 20 mSv. In addition, every low dose CT scan adds 3 mSv to the radiation burden.

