5.2.6.1.4 Adverse events of special interest (AESIs)

The term AESI relates to any specific AE that has been identified at the project level as being of Particular concern for prospective safety monitoring and safety assessment within this trial, e.g. the potential for AEs based on knowledge from other compounds in the same class. AESIs need to be reported to the sponsor’s Pharmacovigilance DePartment within the same timeframe that applies to SAEs, please see above.

The following are considered as AESIs: irAEs, infusion-related AEs, potential DILI events, and hepatic injury are AESIs (see below).

Immune-related adverse events (irAEs)

Immune-related AEs are AEs associated with immunotherapy treatments that appear to be associated with the immune therapy’s mechanism of action. These adverse reactions, which can be severe, may involve the gastrointestinal, skin, liver, endocrine, respiratory, renal, or other organ systems. All immune-relate events are to be reported as AEs. Some irAEs also need to be reported as AESIs as defined by the sponsor in [Table 10.1: 1](#). If an Investigator determines a grade 3 event (not on the list) to be immune-related, the Investigator should also report that event as an AESI.

Recommendations for the management of irAEs are presented in [Appendix 10.2](#).

Infusion-related reactions

To reduce the risk of IRRs, patients are to be pre-treated with an antihistamine and acetaminophen or paracetamol. Pre-treatment should be administered at sufficient time prior to initiation of infusion to allow the agents to exert their effect.

In the event of an infusion-related reaction ≤ Grade 2, treat the symptoms accordingly with antihistamine or corticosteroids if needed, the infusion rate of BI 754111 and/or the

Proprietary confidential information © 2020 Boehringer Ingelheim International GmbH or one or more of its affiliated companies

combination of BI 754111 plus BI 754091 may be decreased by 50% or interrupted until resolution of the event and re-initiated at 50% of the initial rate until completion of the infusion. In patients experiencing infusion-related reactions \leq Grade 2, subsequent infusions may be administered at 50% of the initial rate. *If an infusion related reaction is Grade 3 or higher in severity at any point during the study, permanently discontinue study drug(s).*

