 - BI 754091 and BI 754111 should be permanently discontinued for any recurrent Grade 3-4 AE, inability to taper steroids to 10 mg or less prednisone or equivalent within 12 weeks, or persistent Grade 2-3 AEs that do not recover to Grade 1 or less within 12 weeks.
- Adrenal insufficiency:
 - BI 754091 and BI 754111 should be permanently discontinued for Grade 3-4 adrenal insufficiency or persistent Grade 2 AEs that do not recover to Grade 1 or less within 12 weeks.
- Rash:
 - BI 754091 and BI 754111 should be permanently discontinued for Grade 4 rash, any recurrent Grade 3 AE or persistent Grade 2-3 AEs that do not recover to Grade 1 or less within 12 weeks.
- Encephalitis:
 - BI 754091 and BI 754111 should be permanently discontinued for any grade encephalitis.
- Infusion reactions:

Signs and symptoms usually develop during or shortly after drug infusion and generally resolve completely within 24 hours of completion of infusion.

In the event of an infusion-related reaction \leq Grade 2, treat the symptoms accordingly with antihistamine or corticosteroids if needed, the infusion rate of study drug(s) may be decreased by 50% or interrupted until resolution of the event and re-initiated at 50% of the initial rate until completion of the infusion. In patients experiencing infusion-related reactions \leq Grade 2, subsequent infusions may be administered at 50% of the initial rate. If an infusion related reaction is Grade 3 or higher in severity at any point during the study, permanently discontinue study drug(s).

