- Investigator assessed drug-related AEs by highest CTCAE grade
- Investigator assessed drug-related SAEs by highest CTCAE grade
- Investigator assessed AEs of special interest (AESIs) by highest CTCAE grade
- irAEs through the whole trial (i.e. including irAEs occurring after residual effect period) by highest CTCAE grade
- Investigator assessed infusion-related AEs by highest CTCAE grade
- AEs leading to treatment discontinuation by highest CTCAE grade

- AEs leading to death

For the definition of irAEs and AESIs refer to the CTP Section 5.2.6.1

The SOC will be sorted by frequency, and preferred terms will be sorted by frequency (within SOC).

Adverse events that are immune mediated can potentially begin more than 30 days after treatment. Additional tables will summarize all immune related events, including events with onset more than 30 days after the last treatment.

AEs leading to death during the on-treatment period will be tabulated by SOC and PT. Reported fatal AEs during follow-up period will be listed. All deaths during the study will be summarized by primary cause of death (death due to disease, death due to AE, death cause unknown, other).

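### AESI rules for unlisted immune-related events conflict: read literally they cover only Grade 3, and encephalitis, a stopping event at any grade, has no entry in the table

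*Protocol*

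**What the plan says.** - **Protocol 5.2.6.1.4** opens by counting immune-related AEs in general among the AESIs, with a pointer to the text below. That text is narrower. All immune-related events are reported as AEs, and some of them are also AESIs, as set out in Table 10.1: 1. For the rest there is one clause: "If an Investigator determines a grade 3 event (not on the list) to be immune-related", it is to be reported as an AESI too.
- **Protocol Table 10.1: 1** states its own status: "This table defines immune-related AEs that must be reported as AESIs". Its last row is headed "Other (report as AESI for any grade") and contains the catch-all item "Any other Grade 3 event that is considered immune-related by the physician".
- **The neurologic row** of that table, "Neurologic (report as AESI for any grade"), names autoimmune neuropathy, Guillain-Barre syndrome, demyelinating polyneuropathy and myasthenic syndrome. Encephalitis is not in this row or any other.
- **Protocol 10.2** says "BI 754091 and BI 754111 should be permanently discontinued for any grade encephalitis". Section 4.1.2.4 and the opening paragraph of 10.2 give the same rule.
- **Protocol 5.2.6.2.2** sets one timeline, 24 hours, for SAEs and AESIs alike.
- **SAP 7.8.1** plans a table of "Investigator assessed AEs of special interest (AESIs) by highest CTCAE grade" and refers to Protocol 5.2.6.1 for the definition.

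**The concern.** AESI status has two uses in this trial: it triggers a 24-hour report to the sponsor, and it decides which patients are counted in one of the SAP's safety tables. For an immune-related event that the table does not name, the protocol gives three incompatible answers: every such event, events of any grade, or Grade 3 events only. The most specific wording, which appears in both places, is also the oddest, because it includes a Grade 3 event and leaves out the same event at Grade 4 or 5.

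Encephalitis shows the problem from the other end. It always ends treatment with both antibodies, yet a site that follows the table has no instruction to report it as an AESI at Grade 1 or 2. If sites resolve the conflict differently from case to case, the AESI count has no fixed meaning.

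**Working it through.** No arithmetic is at issue in the rule itself, so the texts are set side by side.

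**Step 1. Which grades of an unlisted immune-related event are AESIs?**

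| Reading | Source | G1 | G2 | G3 | G4 | G5 |
|---|---|---|---|---|---|---|
| Literal catch-all | 5.2.6.1.4 clause; *Other* row item | no | no | yes | no | no |
| Grade 3 or higher | not written for unlisted events; probable intent | no | no | yes | yes | yes |
| General sentence, or row heading taken alone | opening of 5.2.6.1.4; *Other* row heading | yes | yes | yes | yes | yes |

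The readings agree only at Grade 3. The literal one differs from the second at two grades and from the third at four. The literal one cannot be dismissed as loose notation, because other rows of the same table use a greater-or-equal sign before Grade 2 or Grade 3, and the haematologic row singles out Grade 4 anaemia.

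**Step 2. Which diagnoses named in the discontinuation rule (4.1.2.4, repeated in 10.2) have an entry in the table?**

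| Diagnosis | Row in Table 10.1: 1 |
|---|---|
| Pneumonitis | Pneumonitis |
| Adrenal insufficiency | Endocrine |
| Colitis | Colitis |
| Diabetes mellitus | Endocrine (type 1, new onset) |
| Hypophysitis | Endocrine |
| Rash | Skin |
| Encephalitis | none |

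Six of seven have an entry. Encephalitis is also the only one of the seven that stops treatment at any grade on first occurrence. The colitis, haematologic, hepatic and ocular rows make an event of any grade an AESI when it leads to a dose modification or systemic steroids, so the omission does not fit the table's own pattern.

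**Step 3. What follows under the literal reading?**

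| Event | 24-hour report | SAP AESI table | Other SAP 7.8.1 tables |
|---|---|---|---|
| Unlisted, immune-related, Grade 4-5 | largely kept, as an SAE (5.2.6.1.2, 5.2.6.2.2) | absent | irAEs by grade; SAEs by grade; AEs leading to death |
| Encephalitis, Grade 1-2, not classed as serious | not required | absent | irAEs by grade, if judged immune-related; AEs leading to discontinuation by grade |
| Encephalitis, Grade 3, judged immune-related | kept | present | as above |

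The irAE table is not tied to the list, since 5.2.6.1.4 defines irAEs by mechanism and the SAP runs that table through the whole trial.

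**Step 4. Rough scale at Grade 4.** Section 1.4 reports 86 patients on the combination and a Grade 4 AE frequency of 1.2%: 0.012 × 86 = 1.03, about one patient. If that rate carried over to the planned maximum of 40 patients, 0.012 × 40 = 0.48 patients would have a Grade 4 event of any cause. The unlisted immune-related subset cannot exceed this. The documents give no rate for encephalitis.

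**The case against.** **The Grade 3 wording is a drafting slip that no site would apply literally.** Probably it is a slip. The general sentence in 5.2.6.1.4 and the any-grade heading both point to a wider reading. But the limit stands in both operative places, and the table marks *or higher* elsewhere when it means it.

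**The events are covered by other routes.** This largely stands and sets the size of the point. Fatal and life-threatening events are SAEs. An important medical event can be made serious on medical judgement, and 5.2.6.1.3 refers to a sponsor list of always-serious events that is not in the documents. If encephalitis is on that list, the reporting gap closes.

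**Nothing requires the AESI list to match the stopping list.** True: 5.2.6.1.4 says AESIs are identified at project level. The encephalitis point is therefore one of consistency with the table's own pattern, not a breach of a stated rule.

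**The trial has ended early.** SAP Section 4 says so, which limits what an amendment could still achieve.

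A reader might also infer three stronger things that the documents do not support:

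- *That the gap has already occurred, with meningitis.* Section 1.4 says of the earlier combination trial that "infusion related reaction (2 cases), aseptic meningitis and maculopapular rash were reported as possibly related to study drugs". Aseptic meningitis is indeed unlisted, but that case was Grade 3, so the catch-all would take it in if it were judged immune-related. No section has an any-grade stopping rule for meningitis, so it is not in the same position as encephalitis.
- *That severe immune-related events drop out of the report.* They do not. They remain in the SAP's irAE, SAE, discontinuation or death tables, and only the AESI label and count are affected.
- *That adding encephalitis would make every discontinuation trigger an AESI.* It would not. Total bilirubin above 3 times ULN alone, recurrent Grade 3-4 AEs and persistent Grade 2-3 AEs are also triggers and are not all on the list.

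**Conclusion.** The point holds in a limited form. The AESI definition for unlisted immune-related events is internally inconsistent, and its most specific wording excludes Grades 4 and 5. Encephalitis is the one named diagnosis in the discontinuation rule with no table entry. The consequence is a misdefined AESI label and AESI-table count and, for a non-serious Grade 1-2 encephalitis, a possible missing 24-hour report. On the figures in Section 1.4 the count would probably change by no more than about one patient at Grade 4.

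This rests on four assumptions: that the specific clause is followed over the general sentence; that Grade 4-5 events largely meet the fatal or life-threatening SAE criteria (the protocol cites CTCAE but does not reproduce its grade definitions); that the Grade 4 rate in the earlier trial is a fair guide; and that encephalitis is not on the unseen always-serious list. It is worth correcting because the rule is operative and the correction is cheap, not because patient safety reporting fails broadly.

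**What to change.** 1. In 5.2.6.1.4 and in the *Other* row of Table 10.1: 1, replace *Grade 3* by *Grade 3 or higher*.
2. Give that catch-all item its own row, so that the any-grade heading no longer applies to it.
3. Add encephalitis to the neurologic row, as an AESI for any grade.
4. Reword the general sentence in 5.2.6.1.4 so that it refers to irAEs as defined in the table and the catch-all.

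If no further amendment is made because of the early termination, apply the same definition in the AESI derivation and state it in the clinical trial report. Because the SAP table uses investigator-assessed AESIs, this means checking the investigator's flag against the reconciled definition and listing any event on which they differ.

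Cost: a few words, one table entry and a few more AESI forms, or one programmed check if done at reporting. No new assessment is needed, and no treatment or stopping rule changes.
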